5.2.1 Analyses for binary data

Descriptive statistics for categorical variables (e.g., proportions) are the percentage (%), with the number of subjects with data on the specified characteristic as the numerator (n), and the number of subjects in the specific analysis set as denominator (N) used in the percentage calculation, and the 95% CIs where applicable.

The exact 95% CI for binary endpoints for each group will be computed using the F distribution (Clopper-Pearson; [Agresti 2002](#)). Unless otherwise stated, the 95% CI for the between-group difference for binary endpoints will be calculated using the Miettinen and Nurminen method ([Miettinen and Nurminen 1985](#)).

For between-group comparison of SR, the difference will be estimated using minimum risk weights and stratified by sex and age group (18 to 55 years, 56 to 85 years). The associated 95% CI will be calculated using stratified Newcombe confidence interval weighted with minimum risk to combine the stratum components and continuity correction.

5.2.2 Analyses for count data

The number of occurrences of a certain event is count data and thus could be modeled using Poisson distribution. The incidence rate is estimated as the number of events observed divided by the total person-years of follow-up.

Assuming an observed event is from Poisson distribution with parameter λT , where λ is the incidence rate and T is the total person-years of follow-up, based on the relationship between the Poisson and chi-square distribution, the exact lower (l) and upper (u) α -percent 2-sided confidence limits for λT can be estimated by:

$$Y_l = \frac{\chi^2_{2Y, \alpha/2}}{2} \quad \text{and} \quad Y_u = \frac{\chi^2_{2(Y+1), 1-\alpha/2}}{2}, \quad \text{respectively,}$$

where Y is the number of events observed.

The exact lower and upper confidence limit for incidence rate λ can then be obtained as Y_l/T and Y_u/T , respectively.

5.2.3 **Analyses for continuous data**

Unless otherwise stated, descriptive statistics for continuous variables are n, mean, median, standard deviation, minimum, and maximum.

5.2.3.1 **Geometric means**

For immunogenicity results the GMTs will be computed along with associated 95% CIs. The geometric mean on NT for each cohort will be calculated separately for all trial parts by exponentiating the mean logarithm of the titers and corresponding CIs based on the Student's t-distribution. Assay results below the LLOQ are set to $0.5 \times \text{LLOQ}$.

5.2.3.2 **Geometric mean fold rises**

Geometric mean fold rise (GMFR) will be defined as the result after vaccination divided by the baseline result. GMFRs are limited to subjects with non-missing values at both time points.

GMFRs will be calculated as the mean of the difference of logarithmically transformed neutralization titers or antibody levels (later result minus earlier result) and exponentiating the mean. The associated 2-sided 95% CIs are obtained by constructing CIs using Student's t-distribution for the mean difference on the natural log scale and exponentiating the confidence limits.

5.2.3.3 **Geometric mean ratios**

For the between-group comparison, adjusted GMRs and the associated 95% CIs will be calculated by exponentiating the difference of least square means and corresponding CIs based on the analysis of logarithmically transformed neutralizing titers. A linear regression model with age, sex, and group (each Part B Cohort versus reference group) will be done. Unadjusted GMRs and the associated 2 sided 95% CIs will be calculated by exponentiating the mean difference of the logarithms of the titers and the corresponding CI (based on the Student's t-distribution).

5.3 **Methods to manage missing data**

Unless otherwise specified, data in summary tables will be presented using Observed Case (OC) data and therefore no missing data will be imputed.

Missing binary and continuous data will be presented only if there is a non-zero count for at least one of the Cohorts.

For endpoints, the missing data handling rules are described in the corresponding endpoint sections.

Handling missing data:

Missing data, other than that described for AE and CM below will not be imputed.

For the purposes of assigning treatment-emergent flag for AEs, partial or missing AE dates will be handled as follows:

- If the day of the month is missing, the onset day will be set to the first day of the month unless it is the same month and year as trial IMP. In this case, to conservatively report the event as treatment-emergent, the onset date will be assumed to be the first date of trial IMP.
- If the onset day and month are both missing, the day and month will be assumed to be 01 January, unless the event occurred in the same year as the trial IMP. In this case, the event onset will be assumed to be the day and month of IMP to conservatively report the event as treatment emergent.
- A completely missing onset date will be assumed to be the first day of trial IMP.

For the purposes of assigning prior or concomitant flag for medications (CM), partial or missing medication dates will be handled as follows:

- If end day is missing and month/year are non-missing, then day is the minimum of treatment end date and the last day of the month.
- If end day/month are missing and year is non-missing, then day is the minimum of treatment end date and the end of the year (31DECYYYY).
- If imputed end date is less than the start date, use the start date as the imputed end date.

Start dates:

- If the start date year is missing, the start date is set to one day prior to treatment start date.
- If the start date year is less than the treatment start date year, then:
 - If the month is missing, the start date is assumed to be mid-year point (01JULYYYY).
 - Else if the month is not missing, the start date is assumed to be mid-month point (15MONYYYY).
- If the start date year value is greater than the treatment start date year, then:
 - If the month is missing, the start date is assumed to be the year start point (01JANYYYY).
 - Else if the month is not missing, the start date is assumed to be the month start point (01MONYYYY).
- If the start date year value is equal to the treatment start date year value:
 - If the month is missing or the month is equal to the treatment start date month, then the start date is assumed to be one day prior to the treatment start date.
 - Else if the month is less than the treatment start date month, the start date is assumed to the mid-month point (15MONYYYY).
 - Else if the month is greater than the treatment start date month, the start date is assumed to be the month start point (01MONYYYY).

For both AE and CM, if complete end date is available and the start date assumed from the steps above is greater than the end date, then the assumed start date should be set to the end date.

6 ANALYSES AND SUMMARIES

6.1 Primary endpoints

6.1.1 Safety endpoints (Part A, Part B and Part C)

If not specified otherwise, all safety analyses will be based on the Safety Set and summarized by Cohort and trial part. The summary analyses post dose 2 and post dose 3 of IMP will be performed with subjects who received two doses and three doses of IMP to calculate the percentages.

6.1.1.1 Safety overview

The number of events, number and percentage of subjects reporting at least one of the below events from IMP administration will be summarized by treatment group post each dose and combined total of events for the periods from each dose up to 1 month after each dose based on Safety Set.

- Solicited local reactions and systemic events
- Any TEAE
- Related TEAE
- TEAE with Grade ≥ 3
- Related TEAE with Grade ≥ 3
- Any solicited AE that starts on Days 1 to 7 and continues longer than 7 d post-vaccination or starts after Day 7 or is an SAE
- Any SAE
- Related SAE
- SAE with Grade ≥ 3
- Related SAE with Grade ≥ 3
- TEAE leading to trial withdrawal
- TEAE leading to treatment withdrawal
- Any AESI
- All cause death

6.1.1.2 Local reactions

The number and percentage of subjects reporting local reactions (pain at the injection site, tenderness, erythema/redness, induration/swelling) within 7 days after each dose will be

summarized by maximum severity and cumulatively across severity levels. The associated 2-sided Clopper-Pearson 95% CI's will also be displayed.

The Reactogenicity Set will be used for local reaction summaries. Subjects without any e-diary data throughout the 7 days after vaccination or have recorded events only beyond 7 days, will be excluded from the local reaction analysis.

In addition, local reactions will also be summarized by:

- Duration (days) of each local reaction after each dose.
- Onset day of each local reaction after each dose.

Bar charts with the proportions of subjects for each local reaction throughout 7 days after each dose will be plotted. The bars will be divided into severity categories to highlight the proportions of subjects by maximum severity. In addition, listing of subjects in the Reactogenicity Set, with reported local reactions, will be provided.

6.1.1.3 Systemic events

Systemic events (fever, fatigue, headache, chills, vomiting, nausea, diarrhea, new or worsened muscle pain, and new or worsening joint pain) reported within 7 days after each dose will be summarized in the same manner as local reactions (see [Section 6.1.1.1](#)) using the Reactogenicity Set. Subjects without any e-diary data throughout the 7 days after vaccination will be excluded from the systemic events analysis. In addition, listing of subjects in the Reactogenicity Set, with reported systemic events, will be provided.

6.1.1.4 Adverse events

The number of events, number and percentage of subjects reporting a treatment-emergent adverse event (TEAE) up to 1 month post each dose will be summarized by system organ class (SOC) and preferred term (PT) in descending order of frequency within both SOC and PT. Where a subject has the same TEAE, based on SOC or PT, reported multiple times in the same category the subject will only be counted once at that system organ class/preferred term.

6.1.1.5 Serious adverse events

The number of events, number and percentage of subjects reporting serious TEAEs and serious related TEAEs up to 6 months after last dose will be summarized in the same manner as the AEs. The non-serious AEs will also be summarized.

6.1.2 Immunogenicity endpoints – Part B

Between-group comparison of Part B Cohort 1, 4 and 6 with subjects from the Phase III trial BNT162-02 / C4591001 trial

To evaluate the primary immunogenicity endpoints for Part B Cohort 1, 4 and 6 using non-inferiority test, separate control groups, one for each cohort in Part B, will be selected from the BNT162-02 / C4591001 trial who received two doses of BNT162b2 and had corresponding immune results at 1 month post 2nd dose. Subjects will only be selected into one of the control groups. Control groups will be randomly selected with matching factors sex and age (in years) to ensure comparable distribution in each cohort. The subject selection is described in [Appendix 2](#).

6.1.2.1 GMR of VOC specific NT at 1 month after 1 dose BNT162b2 (B.1.1.7 + B.1.617.2) in BNT162b2 experienced subjects vs reference strain NT at 1 month after 2 doses of BNT162b2 (Cohort 1 vs subjects from the Phase III trial BNT162-02 / C4591001)

The number of subjects with valid and determinate assay results for the specified assay at each given dose/sampling time point, GMT, GMR and the associated 2-sided 95% CIs will be provided for each of Cohort 1 VOC (B.1.1.7 + B.1.617.2) strains vs subjects from the Phase III trial BNT162-02/C4591001 reference strain.

GMRs and associated 2-sided 95% CIs will be calculated using linear regression model as described in [Section 5.2.3.3](#).

Below sensitivity analyses may be performed as appropriate:

1. Unadjusted GMR and 95% CI based on student t-distribution using the Immunogenicity Analysis Set.
2. Adjusted GMR and 95% CI in subjects, without evidence of SARS-CoV-2 infection up to one-month after 1 dose of BNT162b2 (B.1.1.7 + B.1.617.2) and up to one-month after the second dose of BNT162b2, with age (in years) and sex as covariates using the Immunogenicity Analysis Set. No evidence of SARS-CoV-2 infection post vaccination is defined in [Section 3.4.1](#).
3. Also, bar plots including LLOQ and ULOQ lines and with different color codes for data from subjects according to their N-binding assessment for the respective visit, time point will be presented.

6.1.2.2 The difference in SRs to VOC specific NT 1 month after 1 dose BNT162b2 (B.1.1.7 + B.1.617.2) to the reference strain NT at 1 month after 2 doses in BNT162b2 (Cohort 1 vs subjects from the Phase III trial BNT162-02 / C4591001)

The number and percentage of subjects with SR at each specified time point and the difference in percentages with 95% CI will be provided for each of Cohort 1 VOC (B.1.1.7 + B.1.617.2) strains and subjects from the Phase III trial BNT162-02/C4591001 reference strain.

Adjusted difference in proportions will be estimated using minimum risk weights and stratified by sex and age group (18 to 55 years, 56 to 85 years) and expressed as a percentage. The associated 2-Sided CI will be based on the Newcombe method stratified by sex and age group (18 to 55 years, 56 to 85 years) with minimum risk weights for the difference in proportions.

Non-inferiority will be assessed sequentially for GMR followed by SR. Non-inferiority will be declared if the lower bound of the 2-sided 95% CI for the difference in percentages of participants with SR is greater than -10%.

Below sensitivity analysis may be performed as appropriate:

1. Unadjusted differences of SR using the Immunogenicity Analysis Set will be calculated as the difference in SRs between VOC and reference. The 95% CI will be obtained using Miettinen and Nurminen Confidence Limits.

2. Adjusted difference in SR for subjects, without evidence of SARS-CoV-2 infection up to one-month after 1 dose of BNT162b2 (B.1.1.7 + B.1.617.2) and up to one month after the second dose of BNT162b2 with age group (18 to 55 years, 56 to 85 years) and sex as covariates using the Immunogenicity Analysis Set.

6.1.2.3 GMR of VOC specific NT at 1 month after 1 dose BNT162b2 (B.1.617.2) vs reference strain NT at 1 month after 2 doses of BNT162b2 (Cohort 4 vs subjects from the Phase III trial BNT162-02 / C4591001)

The number of subjects with valid and determinate assay results for the specified assay at each given dose/sampling time point, GMT, GMR and the associated 2-sided 95% CIs will be provided for Cohort 4 VOC (B.1.617.2) strain vs subjects from the Phase III trial BNT162-02/C4591001 reference strain.

GMRs and associated 2-sided 95% CIs will be calculated using linear regression model as described in [Section 5.2.3.3](#).

Below sensitivity analyses may be performed as appropriate:

1. Unadjusted GMR and 95% CI based on student t-distribution using the Immunogenicity Analysis Set.
2. Adjusted GMR and 95% CI subjects, without evidence of SARS-CoV-2 infection up to one-month after 1 dose of BNT162b2 (B.1.617.2) and up to one month after the second dose of BNT162b2 with age (in years) and sex as covariates using the Immunogenicity Analysis Set.

Also, bar plots including LLOQ and ULOQ lines and with different color codes for data from subjects according to their N-binding assessment for the respective visit, time point will be presented.

6.1.2.4 The difference in SRs to VOC specific NT 1 month after 1 dose BNT162b2 (B.1.617.2) to the reference strain NT at 1 month after 2 doses in BNT162b2 (Cohorts 4 vs subjects from the Phase III trial BNT162-02 / C4591001)

The number and percentage of subjects with SR at each specified time point and the difference in percentages with 95% CI will be provided for Cohort 4 VOC (B.1.617.2) strain and subjects from the Phase III trial BNT162-02/C4591001 reference strain.

The adjusted difference in percentages will be estimated using minimum risk weights and stratified by sex, age group (18 to 55 years, 56 to 85 years). The associated 95% CI will be calculated using stratified Newcombe confidence interval weighted with minimum risk to combine the stratum components and continuity correction.

Non-inferiority will be assessed sequentially for GMR followed by SR. Non-inferiority will be declared if the lower bound of the 2-sided 95% CI for the difference in percentages of participants with SR is greater than -10%.

Below sensitivity analysis may be performed as appropriate:

1. Unadjusted differences of SR using the Immunogenicity Analysis Set will be calculated as the difference in SRs between VOC and reference. The 95% CI will be obtained using Miettinen and Nurminen Confidence Limits.

2. Adjusted difference in SR for subjects, without evidence of infection up to one-month after 1 dose of BNT162b2 (B.1.617.2) and up to one month after the second dose of BNT162b2 with age group (18 to 55 years, 56 to 85 years) and sex as covariates using the Immunogenicity Analysis Set.

6.1.2.5 GMR of reference strain NT at 3 weeks after 1 dose of BNT162b2 (B.1.1.7 + B1.617.2) vs reference strain NT at 1 month after 2 doses of BNT162b2 in COVID-19 vaccine-naïve subjects (Cohort 6 with prior infection vs BNT162-02 / C4591001 without infection)

The number of subjects with valid and determinate assay results for the specified assay at each given dose/sampling time point, GMT, GMR and the associated 2-sided 95% CIs will be provided.

Adjusted GMRs and associated 2-sided 95% CIs will be calculated using linear regression model as described in [Section 5.2.3.3](#). Non-inferiority will be declared if the lower bound of the 2-sided 95% CI for GMR is >0.67 .

Two sensitivity analyses will be performed:

1. Unadjusted GMR and 95% CI based on the student t-distribution using the Immunogenicity Analysis Set.
2. Unadjusted GMR and 95% CI based on the student t-distribution using the All-available Immunogenicity Set (mITT), if there is a meaningful difference in the populations.

6.1.2.6 SR to reference strain NT 3 weeks after 1 dose of BNT162b2 (B.1.1.7 + B1.617.2) vs SR to the reference strain NT at 1 month after 2 doses of BNT162b2 in COVID-19 vaccine-naïve subjects (Cohort 6 with prior infection vs BNT162-02 / C4591001 without infection)

The number and percentage of subjects with SR at each specified time point and the difference in percentages with 95% CI will be provided.

The adjusted difference in percentages will be estimated using minimum risk weights and stratified by sex and age group (18 to 55 years, 56 to 85 years). The associated 95% CI will be calculated using stratified Newcombe confidence interval weighted with minimum risk to combine the stratum components and continuity correction.

Non-inferiority will be assessed sequentially for GMR followed by SR. Non-inferiority will be declared if the lower bound of the 2-sided 95% CI for the difference in percentages of participants with SR is greater than -10%.

Two sensitivity analyses will be performed:

1. Unadjusted difference in SR and the 95% CI calculated using Miettinen and Nurminen method on Immunogenicity Analysis Set.
2. Unadjusted difference in SR and the 95% CI calculated using Miettinen and Nurminen method on All-available Immunogenicity Set (mITT), if there is a meaningful difference in the populations.

6.1.2.7 GMR of VOC specific NT at 1 month after 2 doses vs reference strain NT at 1 month after 2 doses in COVID-19 vaccine-naïve subjects (Cohort 6 vs subjects from the Phase III trial BNT162-02 / C4591001)

The non-inferiority test for this primary immunogenicity endpoint and associated sensitivity analyses will not be performed. The details of clinical and statistical considerations are described in [Section 8.2](#).

6.1.2.8 SR to VOC specific NT 1 month after 2 doses vs SR to the reference strain NT at 1 month after 2 doses in COVID-19 vaccine-naïve subjects (Cohort 6 vs subjects from the Phase III trial BNT162-02 / C4591001)

The non-inferiority test for this primary immunogenicity endpoint and associated sensitivity analyses will not be performed. The details of clinical and statistical considerations are described in [Section 8.2](#).

6.1.3 Immunogenicity endpoints – Part C

6.1.3.1 GMR of VOC specific NT at 1 month after 1 dose of BNT162b2 (B.1.1.529) to those at 1 month after one dose of BNT162b2 for Cohorts 7 and 8

The number of subjects with valid and determinate assay results for the specified assay at each given dose/sampling time point, GMT, GMR and 95% CI by Cohort the associated 2-sided 95% CIs will be provided.

The between group comparison using linear regression model with age and number of prior doses as covariates based on Immunogenicity Analysis Set will be done.

1. Unadjusted GMR will be calculated without age and number of doses based on the student t-distribution using Immunogenicity Analysis Set as sensitivity analysis.

6.1.3.2 SR to VOC specific NT at 1 month after 1 dose of BNT162b2 (B.1.1.529) vs SR to those at 1 month after one dose of BNT162b2 for Cohorts 7 and 8

The number and percentage of subjects with SR at each time point and the difference in percentages with 95% CI will be provided by Cohort.

The adjusted difference in percentages will be estimated using minimum risk weights and stratified by age group and number of prior doses based on Immunogenicity Analysis Set. The associated 95% CI will be calculated using stratified Newcombe confidence interval weighted with minimum risk to combine the stratum components and continuity correction.

1. Unadjusted SR will be calculated without age and number of doses and the 95% CI will be calculated using Miettinen and Nurminen method on Immunogenicity Analysis Set as sensitivity analysis.

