Issue/train and collect e-diary		Issue/train	Collect					Collect	

Activity	Visit 0	Visit 1	Visit 2	Visit 3	Visit 4	Visit 5	Visit 6/ EOT	Early termination	COVID-19
Visit description	Screening	Pre-Vax (except IMP injection)	1 wk Post-Vax FU	1 mon Post-Vax FU	3 mon Post-Vax FU	6 mon Post-Vax FU	1 yr Post-Vax FU		Ad hoc
Day (relative to Visit 1 on Day 1)	-7 to -1	1	8+2	29±3	85±5	180±10	360±10		
Subjects report daily reactivity (incl. oral body temperature) for 7 days after dosing using an e-diary		Start after Vax	End						
Review e-diary data		Start	End						
Record any AEs, AESIs, or SAEs since last visit h		X	X	X	X e	X e	X e	X e	X e
Oral swabs for NAAT-based SARS-CoV-2 for surveillance			X	X	X	X	X	X	X
Oral swabs for SARS-CoV-2 sequencing d	X	X	X	X	X	X	X	X	X
Blood draws for serological testing for SARS-CoV-2 N-binding antibodies and for humoral immunogenicity assessments (30 mL) f		X	X	X	X	X	X	X	X j
SARS-CoV-2 N-binding antibodies assessment (5 mL) n	X								
Blood draws for T- and B-cell responses (135 mL) i		X	X	X	X	X	X		X j
Blood draw for HLA		X k							
Record pregnancies		Start	=>	=>	=>	=>	End	End	

Note: The SoA allows for *ad hoc* visits for SARS-CoV-2 testing for symptomatic or asymptomatic subjects.

a At Visit 0: complete physical examination including body weight and vital signs (oral body temperature, heart rate, blood pressure [systolic and diastolic]); at Visit 1: symptom-orientated physical examination.

- b If the result from an oral swab for NAAT-based SARS-CoV-2 is not older than 24 h at the planned time of IMP injection, availability of the test result from Visit 1 on Day 1 is optional.
- c Issue thermometer or other measuring device for subjects to measure their oral body temperature each day and if they experience flu-like symptoms.
- d All swabs will be analyzed, even if no COVID-19 symptoms are shown.
- e For any visits >1 month after each IMP injection, only IMP-related AEs, trial procedure-related AEs, AESIs, any SAEs. In addition, all AEs linked to confirmed COVID-19 cases will be recorded.
- f Blood samples will be stored and may be analyzed retrospectively for additional clinical parameters (troponin, cytokine).
- g The 12-lead ECG at Visit 1 can be skipped if the 12-lead ECG from Visit 0 was performed within 24 h prior to the planned IMP dose.

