To describe the humoral immune response against SARS-CoV-2 variants after one dose of BNT162b2 (B.1.1.529) or after one dose of BNT162b2 or a post SARS-CoV-2 infection in RNA-based COVID-19 vaccine-experienced subjects with history of SARS-CoV-2 infection.	
 
GMT of VOC NT at baseline and 7 days, 1 month, and 3 months after the trial start for Cohorts 7, 8, and 9, and 6 and 12 months after the trial start for Cohorts 7 and 8.
 
	
 
VOC specific NTs
 

OBJECTIVES	ESTIMANDS	ENDPOINTS
Exploratory objectives		
To evaluate SARS-CoV-2 viral sequences in subjects.	
 
SARS-CoV-2 S antigen sequences or whole viral genome sequencing of interest.
 
	
 
Viral sequences
 

To evaluate cross-neutralization of vaccine-induced antibodies to ancestral and emerging SARS-CoV-2 variants.	
 
For a subset of subjects, after one dose of monovalent vaccine BNT162b2 (B.1.1.529) or BNT162b2, measured cross-neutralization of other SARS-CoV-2 variants (e.g., using VNT or pVNT).
 
	
 
NT data
 

To evaluate the immune response over time to prophylactic monovalent vaccine BNT162b2 (B.1.1.529) or BNT162b2 and persistence of immune response in RNA-based COVID-19 vaccine-experienced subjects with history of SARS-CoV-2 infection.	
 
GMC/GMT and GMFR at baseline, 7 days, and 1, 3, 6, and 12 months after completion of vaccination.
 
Seroresponse for B.1.1.529 variant strain.
 
	
 
Reference and VOC specific NTs
 
RBD and full length S-binding or S1-binding Ig levels
 

To evaluate the immune response to SARS-CoV-2 in subjects.	
 
GMC/GMT and GMFR at baseline, 7 days, and 1, 3, 6, and 12 months after completion of vaccination.
 
	
 
Nucleocapsid (N)-binding Ig levels
 

To describe the incidence of confirmed COVID-19 at 1 year follow-up period in subjects who received one dose of monovalent BNT162b2 (B.1.1.529) or BNT162b2.	
 
Incidence of confirmed COVID-19 cases per 1,000 person-years of follow-up.
 
	
 
Number of confirmed COVID-19 cases
 

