### 10.9.4 Amendment 4.0 (update from protocol version 4.0 to 5.0)

This update implements a change in eligibility criteria for Part C. Eligibility criteria were updated to correspond to the existing regulatory guidance, clarifying the required time

frame between the last dose of the COVID-19 RNA-based vaccine and first IMP dose. The two-month window between the documented SARS-CoV-2 infection and trial IMP administration was implemented to reduce heterogeneity in baseline VNT levels which may affect immune responses after trial vaccine administration. The mandatory NAAT test as a confirmation of prior SARS-CoV-2 infection was adjusted according to suggested updated algorithms for SARS-CoV-2 infection diagnostics.

In addition, based on the recent immunogenicity data from the BNT162b2 Omicron variant vaccine in the BNT162-16 trial, the sample size and expected GMR have been adjusted accordingly.

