The baseline value used in the derivation of geometric mean fold rise (GMFR), SR, and difference of SR for Part A, Part B and Part C of the trial is the value before first dose of trial IMP.

Baseline SARS-CoV-2 infection status:

For Part A and Part B, baseline SARS-CoV-2 infection is defined as below:

Positive:

- if any one of the 3 tests, i.e., nucleocapsid-binding antibody seroconversion, central NAAT, or local NAAT, is positive,
- OR
- had medical history (MH) or AE of COVID-19 prior to vaccination.

Negative:

- no MH or AE of COVID-19 prior to vaccination,
- AND
- negative N-binding.

AND

- both local and central NAAT negative or one negative and one missing.

Missing/indeterminate:

- no MH or AE of COVID-19 prior to vaccination,

AND

- no positive test results from any of the 3 tests,

AND

- N-binding missing or both NAAT missing.

Evidence of SARS-CoV-2 infection post vaccination

No evidence of SARS-CoV-2 infection post vaccination for subjects in Part B is defined as subjects who had no serological or virological evidence of SARS-CoV-2 infection (i.e., negative N-binding antibody [serum] result and negative NAAT [oral swab] at all planned visits and any unscheduled visit (up to the 1-month post–Dose 2 blood sample collection for Cohort 6 and 1-month post–trial vaccination blood sample collection for Cohort 1 and Cohort 4) and had no medical history or AE of COVID-19 (up to the 1-month post–Dose 2 blood sample collection for Cohort 6 and 1-month post–trial vaccination blood sample collection for Cohort 1 and Cohort 4)).

No evidence of SARS-CoV-2 infection post vaccination for subjects from Phase III trial BNT162-02 / C4591001 is defined as subjects who had no serological or virological evidence (up to the 1-month post–Dose 2 blood sample collection) of SARS-CoV-2 infection (i.e., negative N-binding antibody [serum] result at the Dose 1 and 1-month post–Dose 2 visits, negative NAAT [nasal swab] at the Dose 1 and Dose 2 visits, and any unscheduled visit (up to the 1-month post–Dose 2 blood sample collection)) and had no medical history of COVID-19.

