An important protocol deviation is a protocol deviation that, in the opinion of the sponsor’s clinician, would materially affect assessment of immunogenicity, e.g., subject receipt of a prohibited vaccine or medication that might affect immune response or a medication error with suspected decrease in potency of the vaccine.

- a) The sampling windows with grace period specified in Table 7 will be used to define the valid samples for Immunogenicity Analysis Set.
 - b) The sampling windows per protocol specified in Table 7 will be used to define the valid samples for Immunogenicity Analysis Per Protocol Set.
 - c) In cohort 9 all randomized subjects who have a valid and determinate immunogenicity result from the blood sample and have no other important protocol deviations that can confound immunogenicity data, will be included in the Immunogenicity Analysis Set.
 - d) Participants with missing baseline data will be included in this population, providing other criteria are met
- Abbreviation: IMP = investigational medicinal product.

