5.1.4.3 Part C

No confirmatory hypothesis testing is planned for Part C.

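### The randomised Part C GMR model (Cohort 7 vs Cohort 8) leaves out the pre-dose BA.1 titer, which is already collected; adding it would sharpen a descriptive estimate at little cost.

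*SAP*

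**What the plan says.** Part C randomises subjects 2:2:1 to Cohorts 7, 8 and 9, stratified by age group and number of prior RNA-vaccine doses (Protocol 4.1, SAP 2.2.1). The primary immunogenicity estimands are the GMR and the seroresponse (SR) difference for BA.1 titers one month after dosing, Cohort 7 against Cohort 8.

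For the GMR, SAP 6.1.3.1 specifies a "linear regression model with age and number of prior doses as covariates". Its one sensitivity analysis drops both covariates. Protocol 9.4.3.1 names a covariate set for Part B only and leaves the detailed methodology to the SAP.

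The pre-dose titer appears in several other places:

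- Protocol 1.3, Table 6, schedules a blood draw for humoral immunogenicity at Visit 1, before injection, in Cohorts 7 and 8.
- The Part C secondary estimand is the "GMT of VOC NT at baseline and 7 days, 1 month, and 3 months after the trial start" (Protocol 3).
- SAP 3.4.1 states that the baseline used in deriving the "difference of SR for Part A, Part B and Part C of the trial is the value before first dose of trial IMP".
- Protocol 10.9.4 explains that the two-month gap between infection and dosing was "implemented to reduce heterogeneity in baseline VNT levels which may affect immune responses after trial vaccine administration".

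On status, SAP 5.1.4.3 says "No confirmatory hypothesis testing is planned for Part C". On missing values, note d to SAP Table 8 says "Participants with missing baseline data will be included in this population, providing other criteria are met", and SAP 5.3 says "Missing data, other than that described for AE and CM below will not be imputed".

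**The concern.** The pre-dose titer measures the same quantity as the outcome, in the same subjects, before treatment. The sponsor's own amendment rationale treats it as something that may influence the response. One Part C primary endpoint (SR) is built on it and the other (GMR) ignores it.

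The eligibility rules leave room for baseline titers to vary. Subjects may have had two or three doses of any authorised RNA vaccine, with the last more than 4 months before randomisation and the latest infection at least 2 months before. No maximum is given for either interval (Protocol 5.1, criterion 14). Age and dose count capture only part of that.

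What is at stake is precision. Because Part C is descriptive, the estimate and its interval are the result. Protocol 4.2 says the comparison may support the choice of booster in this population. In a linear model on log titer, adding a pre-dose covariate leaves the GMR being estimated unchanged and removes outcome variation that baseline explains. It also corrects for a chance baseline imbalance between two arms of about 80.

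**Working it through.** **Inputs from the documents** (Protocol 9.2.3 and Table 13; SAP 5.1.3.3): 80 evaluable per arm, SD 1.0 on the log scale, assumed GMR 1.75, one-sided alpha 0.025, stated power 94%.

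**Input not in the documents:** the partial correlation r between pre-dose and 1-month log titer, given age and prior doses. Assumed range: 0.2, 0.3, 0.5, 0.7. The SD of 1.0 is taken as the value before baseline adjustment.

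**1. The plan's own figure.**
SE₀ = 1.0 × √(2/80) = 0.1581.
Power = Φ(ln 1.75 / 0.1581 − 1.96) = 94.3%. With a noncentral t on 158 df it is 94.0%. The stated 94% reproduces.

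**2. Effect of adding baseline.**
SE = SE₀ × √(1 − r²); power = Φ(ln 1.75 / SE − 1.96); equivalent n per arm = 80 / (1 − r²); CI = 1.75 × exp(±1.96 × SE).

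| r | SE | Log-scale CI narrower by | Equivalent n per arm | Power at GMR 1.75 | 95% CI if observed GMR is 1.75 |
|---|---|---|---|---|---|
| 0 (current) | 0.1581 | – | 80 | 94.3% | 1.28–2.39 |
| 0.2 | 0.1549 | 2% | 83 | 95.1% | 1.29–2.37 |
| 0.3 | 0.1508 | 5% | 88 | 96.0% | 1.30–2.35 |
| 0.5 | 0.1369 | 13% | 107 | 98.3% | 1.34–2.29 |
| 0.7 | 0.1129 | 29% | 157 | 99.9% | 1.40–2.18 |

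Estimating one more coefficient inflates the variance by about 0.7% (1 + 1/153 = 1.0065), which is not included in the table. Every interval in the table excludes 1.

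**3. Effect of a chance imbalance.** Suppose the arms differ in mean baseline by 2 SE, that is 2 × 0.1581 = 0.32 SD. The current GMR then moves by a factor exp(r × 0.3162) = 1.07, 1.10, 1.17 or 1.25 for the four values of r. An imbalance at least this large, in either direction, has a probability of about 5%.

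**4. Whether the planned fold rises do the same job.** SAP 6.3.3.1 plans within-cohort GMFRs, and a reader could divide one by the other. If the SD is the same at both time points (an assumption) and the correlation is r, a change-score comparison has variance 2(1 − r) relative to the unadjusted one. That is 1.6, 1.4, 1.0 and 0.6 for r = 0.2, 0.3, 0.5, 0.7. Covariate adjustment has 1 − r² = 0.96, 0.91, 0.75 and 0.51. The change score is less precise than covariate adjustment throughout, and less precise than ignoring baseline when r is below 0.5.

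**The case against.** The case for leaving the plan alone is reasonable. Age and number of prior doses correspond to the randomisation factors, and a model prespecified on them is legitimate. The estimate is unbiased, no decision rule depends on it, and at the planned GMR the interval excludes 1 with or without the covariate. The gain depends on a correlation that the documents do not give. The two-month infection window already narrows the baseline spread by design, which other things equal would lower that correlation. Baseline GMTs and GMFRs by cohort will be reported, so an imbalance would be visible. Chance imbalance is not a separate harm, because it is already part of the variance behind the current interval. Finally, the SAP is at version 5 (23 Feb 2024), after the global end of trial on 04 October 2023, so changing a primary model now carries its own risk.

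Most of this stands as a limit on the size of the point. The imbalance figures describe the same uncertainty as the interval width and should not be added to it. The late timing decides which form of the fix is appropriate.

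None of it removes the point. The window reduces heterogeneity without eliminating it. Reported baseline GMTs and within-cohort GMFRs do not give a baseline-adjusted comparison between arms, and step 4 shows that a ratio of GMFRs is a poor substitute.

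**Conclusion.** The concern holds as a recommended improvement. SAP 6.1.3.1 omits a pre-dose measurement that is already collected, is used for the companion primary endpoint, and is linked by the sponsor to the response. The cost is some precision in a descriptive primary estimate. It creates no bias, breaks no success rule and does not make the 94% wrong.

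The size rests on the assumed r, SD 1.0 and 80 per arm. The interval narrows by 2% to 29% for r from 0.2 to 0.7, with 13% at r = 0.5. At the low end the gain is negligible. That the covariate is omitted is certain; the benefit of adding it can only be given as a range.

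**What to change.** In SAP 6.1.3.1:

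- Add the natural-log Visit 1 BA.1 titer as a covariate beside age and number of prior doses, with values below LLOQ set to 0.5 × LLOQ as in SAP 5.2.3.1.
- State a rule for subjects with no baseline value, since note d to Table 8 admits them. Either use a missing-indicator term, written as an explicit exception to the no-imputation rule in SAP 5.3, or analyse observed cases and report how many are missing.
- Keep both the current age-plus-doses model and the unadjusted GMR as sensitivity analyses.

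The documents do not say whether Part C titers by cohort had been seen when SAP version 5 was signed. If they had, leave the primary model as written and report the baseline-adjusted GMR as a supplementary analysis, labelled as such.

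The cost is one covariate, one sentence on missing baselines and one extra table row. No new samples or assays are needed.
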